13.0 QUALITY CONTROL AND QUALITY ASSURANCE

13.1 Study-Site Monitoring Visits

Monitoring visits to the study site will be made periodically during the study to ensure that all aspects of the protocol are followed. Source documents will be reviewed for verification of data recorded on the eCRFs. Source documents are defined as original documents, data, and records. The investigator and institution guarantee access to source documents by the sponsor or its designee (contract research organization) and by the IRB or IEC.

All aspects of the study and its documentation will be subject to review by the sponsor or designee (as long as blinding is not jeopardized), including but not limited to the Investigator's Binder, study medication, subject medical records, informed consent documentation, documentation of subject authorization to use personal health information (if separate from the ICFs), and review of eCRFs and associated source documents. It is important that the investigator and other study personnel are available during the monitoring visits and that sufficient time is devoted to the process.

13.2 Protocol Deviations

The investigator should not deviate from the protocol, except where necessary to eliminate an immediate hazard to study subjects. Should other unexpected circumstances arise that will require deviation from protocol-specified procedures, the investigator should consult with the sponsor or designee (and IRB or IEC, as required) to determine the appropriate course of action. There will be no exemptions (a prospectively approved deviation) from the inclusion or exclusion criteria.

The site should document all protocol deviations in the subject's source documents. In the event of a significant deviation, the site should notify the sponsor or its designee (and IRB or EC, as required). Significant deviations include, but are not limited to, those that involve fraud or misconduct, increase the health risk to the subject, or confound interpretation of primary study assessment. A Protocol Deviation Form should be completed by the site and signed by the sponsor or designee for any significant deviation from the protocol.

Every attempt will be made to collect each PK blood sample at the designated time point, and the actual time of each blood sample will be recorded on the source document and eCRF. Table 8 defines the windows allowed for sample collections.

Protocol Deviation Forms are to be completed for PK samples collected outside of the following intervals:

Table 8 Windows for PK Blood Sample Collection

Minutes	Nominal Sampling Time
Pre-dose	Pre-dose (0 h)
±5	immediately post-dose to ≤6 h
±15	>6 h to ≤12 h post-dose
±60	>12 h post-dose

Study No. CVN424-201 Page 63 of 73

Protocol v. 4.0 14 July 2021

13.3 Quality Assurance Audits and Regulatory Agency Inspections

The study site also may be subject to quality assurance audits by the sponsor or designees. In this circumstance, the sponsor-designated auditor will contact the site in advance to arrange an auditing visit. The auditor may ask to visit the facilities where laboratory samples are collected, where the medication is stored and prepared, and any other facility used during the study. In addition, there is the possibility that this study may be inspected by regulatory agencies, including those of foreign governments (e.g., the FDA, the United Kingdom Medicines and Healthcare products Regulatory Agency, the Pharmaceuticals and Medical Devices Agency of Japan). If the study site is contacted for an inspection by a regulatory body, the sponsor should be notified immediately. The investigator and institution guarantee access for quality assurance auditors to all study documents as described in Section 13.1.

Study No. CVN424-201 Page 64 of 73

Protocol v. 4.0 14 July 2021

14.0 ETHICAL ASPECTS OF THE STUDY

This study will be conducted with the highest respect for the individual participants (i.e., subjects) according to the protocol, the ethical principles that have their origin in the Declaration of Helsinki, and the ICH Harmonised Tripartite Guideline for GCP. Each investigator will conduct the study according to applicable local or regional regulatory requirements and align his or her conduct in accordance with the "Responsibilities of the Investigator" that are listed in Appendix B. The principles of Helsinki are addressed through the protocol and through appendices containing requirements for informed consent and investigator responsibilities.

14.1 IRB and/or IEC Approval

IRBs and IECs must be constituted according to the applicable state and federal/local requirements of each participating region. The sponsor or designee will require documentation noting all names and titles of members who make up the respective IRB or IEC. If any member of the IRB or IEC has direct participation in this study, written notification regarding his or her abstinence from voting must also be obtained. Those Americas sites unwilling to provide names and titles of all members due to privacy and conflict of interest concerns should instead provide a Federal Wide Assurance Number or comparable number assigned by the Department of Health and Human Services.

The sponsor or designee will supply relevant documents for submission to the respective IRB or IEC for the protocol's review and approval. This protocol, the Investigator's Brochure, a copy of the ICFs, and, if applicable, subject recruitment materials and/or advertisements and other documents required by all applicable laws and regulations, must be submitted to a central or local IRB or IEC for approval. The IRB's or IEC's written approval of the protocol and subject informed consent must be obtained and submitted to the sponsor or designee before commencement of the study (i.e., before shipment of the sponsor-supplied drug or study specific screening activity). The IRB or IEC approval must refer to the study by exact protocol title, number, and version date; identify versions of other documents (e.g., ICF) reviewed; and state the approval date. The sponsor will ship drug/notify site once the sponsor has confirmed the adequacy of site regulatory documentation and, when applicable, the sponsor has received permission from competent authority to begin the trial. Until the site receives drug/notification no protocol activities, including screening may occur.

Sites must adhere to all requirements stipulated by their respective IRB or IEC. This may include notification to the IRB or IEC regarding protocol amendments, updates to the ICF, recruitment materials intended for viewing by subjects, local safety reporting requirements, reports and updates regarding the ongoing review of the study at intervals specified by the respective IRB or IEC, and submission of the investigator's final status report to IRB or IEC. All IRB and IEC approvals and relevant documentation for these items must be provided to the sponsor or its designee.

Subject incentives should not exert undue influence for participation. Payments to subjects must be approved by the IRB or IEC and sponsor.

14.2 Subject Information, Informed Consent, and Subject Authorization

Written consent documents will embody the elements of informed consent as described in the Declaration of Helsinki and the ICH Guidelines for GCP and will be in accordance with all

Study No. CVN424-201 Page 65 of 73

Protocol v. 4.0 14 July 2021

applicable laws and regulations. The ICF, subject authorization form (if applicable), and subject information sheet (if applicable) describe the planned and permitted uses, transfers, and disclosures of the subject's personal and personal health information for purposes of conducting the study. The ICF and the subject information sheet (if applicable) further explain the nature of the study, its objectives, and potential risks and benefits, as well as the date informed consent is given. The ICF will detail the requirements of the participant and the fact that he or she is free to withdraw at any time without giving a reason and without prejudice to his or her further medical care.

The investigator is responsible for the preparation, content, and IRB or IEC approval of the ICF and if applicable, the subject authorization form. The ICF, subject authorization form (if applicable), and subject information sheet (if applicable) must be approved by both the IRB or IEC and the sponsor prior to use.

The ICF, subject authorization form (if applicable), and subject information sheet (if applicable) must be written in a language fully comprehensible to the prospective subject. It is the responsibility of the investigator to explain the detailed elements of the ICF, subject authorization form (if applicable), and subject information sheet (if applicable) to the subject. Information should be given in both oral and written form whenever possible and in the manner deemed appropriate by the IRB or IEC. In the event the subject is not capable of rendering adequate written informed consent, then the subject's legally acceptable representative may provide such consent for the subject in accordance with applicable laws and regulations.

The subject, or the subject's legally acceptable representative, must be given ample opportunity to: (1) inquire about details of the study and (2) decide whether or not to participate in the study. If the subject, or the subject's legally acceptable representative, determines he or she will participate in the study, then the ICF and subject authorization form (if applicable) must be signed and dated by the subject, or the subject's legally acceptable representative, at the time of consent and prior to the subject entering into the study. The subject or the subject's legally acceptable representative should be instructed to sign using their legal names, not nicknames, using blue or black ballpoint ink. The investigator must also sign and date the ICF and subject authorization (if applicable) at the time of consent and prior to subject entering into the study; however, the sponsor may allow a designee of the investigator to sign to the extent permitted by applicable law.

Once signed, the original ICF, subject authorization form (if applicable), and subject information sheet (if applicable) will be stored in the investigator's site file. The investigator must document the date the subject signs the informed consent in the subject's medical record. Copies of the signed ICF, the signed subject authorization form (if applicable), and subject information sheet (if applicable) shall be given to the subject.

All revised ICFs must be reviewed and signed by relevant subjects or the relevant subject's legally acceptable representative in the same manner as the original informed consent. The date the revised consent was obtained should be recorded in the subject's medical record, and the subject should receive a copy of the revised ICF.

Subjects who consented and provided a pharmacogenomic sample for DNA analysis can withdraw their consent and request disposal of a stored sample at any time prior to analysis. Notify sponsor of consent withdrawal.

Study No. CVN424-201 Page 66 of 73

Protocol v. 4.0 14 July 2021

14.3 Subject Confidentiality

The sponsor and designees affirm and uphold the principle of the subject's right to protection against invasion of privacy. Throughout this study, a subject's source data will only be linked to the sponsor's clinical study database or documentation via a unique identification number. As permitted by all applicable laws and regulations, limited subject attributes, such as sex, age, or date of birth, and subject initials may be used to verify the subject and accuracy of the subject's unique identification number.

To comply with ICH Guidelines for GCP and to verify compliance with this protocol, the sponsor requires the investigator to permit its monitor or designee's monitor, representatives from any regulatory authority (e.g., FDA, Medicines and Healthcare products Regulatory Agency, Pharmaceuticals and Medical Devices Agency), the sponsor's designated auditors, and the appropriate IRBs and IECs to review the subject's original medical records (source data or documents), including, but not limited to, laboratory test result reports, ECG reports, admission and discharge summaries for hospital admissions occurring during a subject's study participation, and autopsy reports. Access to a subject's original medical records requires the specific authorization of the subject as part of the informed consent process (see Section 14.2).

Copies of any subject source documents that are provided to the sponsor must have certain personally identifiable information removed (i.e., subject name, address, and other identifier fields not collected on the subject's eCRF).

14.4 Publication, Disclosure, and Clinical Trial Registration Policy

14.4.1 Publication and Disclosure

The investigator is obliged to provide the sponsor with complete test results and all data derived by the investigator from the study. During and after the study, only the sponsor may make study information available to other study investigators or to regulatory agencies, except as required by law or regulation. Except as otherwise allowable in the Clinical Study Site Agreement, any public disclosure (including publicly accessible websites) related to the protocol or study results, other than study recruitment materials and/or advertisements, is the sole responsibility of the sponsor.

The sponsor may publish any data and information from the study (including data and information generated by the investigator) without the consent of the investigator. Manuscript authorship for any peer-reviewed publication will appropriately reflect contributions to the production and review of the document. All publications and presentations must be prepared in accordance with this section and the Clinical Study Site Agreement. In the event of any discrepancy between the protocol and the Clinical Study Site Agreement, the Clinical Study Site Agreement will prevail.

The sponsor may publish any data and information from the study (including data and information generated by the investigator) without the consent of the investigator.

14.4.2 Clinical Trial Registration

In order to ensure that information on clinical trials reaches the public in a timely manner and to comply with applicable laws, regulations, and guidance, the sponsor will register this clinical trial on

Study No. CVN424-201 Page 67 of 73

Protocol v. 4.0 14 July 2021

ClinicalTrials.gov (and possibly on other publicly accessible websites) within 21 days after the first participant is consented.

Sponsor contact information, along with investigator's city, state (for North American investigators), country, and recruiting status will be registered and available for public viewing. For some registries, sponsor will assist callers in locating trial sites closest to their homes by providing the investigator name, address, and phone number to callers requesting trial information. Once subjects receive investigator contact information, they may call the site and request enrollment into the trial. The investigative sites are encouraged to handle such trial inquiries according to their established subject screening process. If the caller asks additional questions beyond the topic of trial enrollment, they should be referred to the sponsor. Any investigator who objects to sponsor providing their contact information to callers must provide sponsor with a written notice requesting that their information not be listed on the registry site.

14.4.3 Clinical Trial Results Disclosure

At the conclusion of the study, the sponsor will post the results on ClinicalTrials.gov or other publicly accessible websites, as required by applicable national and local laws and/or regulations.

14.5 Insurance and Compensation for Injury

Each subject in the study must be insured in accordance with the regulations applicable to the site where the subject is participating. If a local underwriter is required, then the sponsor or sponsor's designee will obtain clinical study insurance against the risk of injury to clinical study subjects. Refer to the Clinical Study Site Agreement regarding the sponsor's policy on subject compensation and treatment for injury. If the investigator has questions regarding this policy, he or she should contact the sponsor or sponsor's designee.

Study No. CVN424-201 Page 68 of 73

Protocol v. 4.0 14 July 2021

Appendix A: Schedule of Study Procedures

Visit Number	SCREE	NING	1	2	3	4	5	6	7	Early Term- ination
Study Day:	Days -28 to -1	Days -2 & -1	Day 0	Day 1	Day 8 ±2 days	Day 15 ±2 days	Day 22 ±2 days	Day 27 ±1 day	Day 35 ±2 days	
Informed consent	X (a)									
Inclusion/exclusion criteria	X									
Demographics	X (a)									
Medical history	X(a)									
Concurrent medical conditions	X (a)									
Medication history	X (a)									
Vital signs and weight (b)	X (a)		X	X	X	X	X	X	X	X
Physical examination	X (a)		X		X			X	X	X
Height and BMI	X (a)							X	X	X
Clinical laboratory tests (c)	X (a)		X	X	X			X	X	X
Screening laboratory tests (d)	X (a)									
Patient Motor Diary (Hauser diary) (e)	X	X				X		X		
Concomitant medications	X		X	X	X	X	X	X	X	X
ECG (f)	X (a)			X	X			X	X	X
Randomization			X							
Study drug dosing (g)				< -	-	-	-	->		
DNA sample collection (h)			X							
RNA collection (i)				X						
PK blood collection (j)				X	X (k)	X	X	X	X	X
PTE assessment (1)	X		X	X						
AE assessment (m)			X	X	X	X	X	X	X	X
Study drug accountability					X	X	X	X	X	X
Unified Parkinson's Disease Rating Scale (UPDRS)			X			X		X	X	X
CGI			X			X		X	X	X
PGI			X			X		X	X	X

Study No. CVN424-201 Page 70 of 73

Protocol v. 4.0 14 July 2021

Visit Number SCREENING		1	2	3	4	5	6	7		
Study Day:	Days -28 to -1	Days -2 & -1	Day 0	Day 1	Day 8 ±2 days	Day 15 ±2 days	Day 22 ±2 days	Day 27 ±1 day	Day 35 ±2 days	Early Term- ination
Epworth Sleepiness Scale			X			X		X	X	X
Questionnaire for Impulsive-Compulsive Disorders (QUIP)			X			X		X		X
Beck Depression Inventory			X					X		X

- (a) Initial Screening items, to be completed prior to other Screening assessments. Screening activities must occur within 28 days of randomization, but may be completed in fewer than 28 days. Screening days are nominally called Day -28 to Day -1, but will not necessarily correspond numerically to the calendar days prior to the Baseline Visit. By the same convention, the Patient Motor Diary will be recorded at home over 2 consecutive days during screening, but not necessarily on the 2 days immediately prior to the Baseline visit (Day 0).
- (b) Vital signs (oral temperature, respiration, heart rate, and blood pressure) and weight will be recorded at Screening, Baseline, Day 1, and at subsequent Study Visits. On Day 1 and Day 8, the assessments will be conducted pre-dose [within 90 minutes prior to dosing], and at least hourly through 3 h post-dose. Triplicate orthostatic vital signs (blood pressure and heart rate) will be recorded 15 minutes apart at baseline. Orthostatic vital signs (non-triplicate) will be recorded pre-dose and at 3 h post-dose on Days 1 and 8. Orthostatic vital signs will be measured after at least 5 minutes supine and again at 2 minutes after standing at each scheduled orthostatic timepoint.
- (c) Clinical laboratory tests (hematology, serum chemistry, urinalysis, and endocrine) will be collected at Screening, Baseline, Day 8, Day 27, Day 35, and Early Termination (if applicable) visits. Urine hCG pregnancy test will be performed on female subjects of childbearing potential on Day 1 prior to dosing.
- (d) Screening laboratory testing will include all items included under 'Clinical Laboratory Tests" plus urine drug & cotinine screen, and for female subjects a serum pregnancy test (hCG). An FSH level will be obtained on post-menopausal women (defined as continuous amenorrhea of at least 2 years and not surgically sterile). One additional tube for plasma and one for serum will be collected for archiving (frozen storage) to support potential post hoc laboratory testing.
- (e) Subjects will receive standardized instruction in how to complete the Patient Motor Diary (Hauser diary). After training, subjects who have passed initial Screening procedures will complete Patient Motor Diary entries for 4 consecutive 30-minute periods during a screening visit while observed and scored by a skilled rater. The concordance testing session must include at least one ON and one OFF period; the test session will extend for up to 4 additional 30 min. periods until there is at least one in each state. Concordance must be within 75% for subject eligibility.
 - Following a successful concordance test and prior to randomization, subjects must complete the Patient Motor Diary at home over 48 h and demonstrate both an acceptable quality of the diary, with no more than 4 errors per day, and average daily OFF time of at least 2 h and not one day below 1.0 h.
 - In advance of Study Visits on Day 15 and 27, subjects will complete Diary entries recording their capabilities, limitations and motor symptoms over the prior 2 days (e.g., Days 13 and 14, or Days 25 and 26).
- (f) Triplicate standard 12-lead ECG will be recorded at Screening and on Days 1 and 8 pre-dose [within 1 h prior to dosing] and 3 h (+/- 15 minutes) post-dose. Triplicate standard 12-lead ECG will also be recorded at screening and on Day 27, Day 35 and Early Termination (if applicable).
- (g) Upon randomization, the first dose of study drug will be administered under direction of site personnel. Near the conclusion of the Day 1 visit and subsequent weekly visits, subjects will be given a supply of study drug (as suspension in amber colored bottles) to be taken home and stored under refrigeration until use. Study drug will be self-administered each morning on days 2-28. However, for scheduled Study Visits on or around day 22, dosing must be deferred until after collection of a blood sample for determination of the study drug "trough" concentration.
- (h) One blood sample will be collected for pharmacogenomic analysis at baseline; this will only be collected once per

Study No. CVN424-201 Page 71 of 73

Protocol v. 4.0 14 July 2021

subject.

- (i) A whole blood sample will be collected pre-dose and 3 h post-dose on Day 1 for RNA pharmacogenomic analysis.
- (j) Blood samples for PK analyses will be collected at timepoints indicated in Table 5.
- (k) At Day 8 visit, one additional tube of blood plasma will be collected for archiving (frozen storage) to support potential post hoc laboratory testing (e.g., biomarkers, potential characterization of unknown CVN424 metabolites).
- (1) PTEs will be collected from signing of informed consent up until dosing on Day 1.
- (m) Any AE with onset or exacerbation after dosing on Day 1 will be captured as an AE.

Study No. CVN424-201 Page 72 of 73

Protocol v. 4.0 14 July 2021

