5.2.2 Secondary Endpoints

The secondary endpoints will include:

- Percentages of subjects with abnormal and clinically significant (CS) safety laboratory test results, ECG test results, or vital sign measurements at least once post-dose
- Change from baseline in 2-day average OFF time at Day 27 as recorded in the Patient Motor Diary

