7.5 Criteria for Discontinuation or Withdrawal of a Subject

The following represent criteria that require discontinuation of study drug and/or withdrawal from the study. The primary reason for discontinuation or withdrawal of the subject from the study or study medication should be recorded in the electronic case report form (eCRF). For screen failure subjects, refer to Section 9.1.15.

- 1. The subject has experienced a pretreatment event (PTE) or AE that requires early termination because continued participation imposes an unacceptable risk to the subject's health or the subject is unwilling to continue because of the PTE or AE.
- 2. Liver Function Test (LFT) abnormalities meeting prespecified criteria.

Study medication should be discontinued immediately with appropriate clinical follow-up (including repeat laboratory tests, until a subject's laboratory profile has returned to normal/baseline status, see Section 9.1.8), if the following circumstances occur at any time during study medication treatment:

Study No. CVN424-201 Page 29 of 73

Protocol v. 4.0 14 July 2021

- ALT or AST >8 × ULN, or
- ALT or AST >5 × ULN and persists for more than 2 weeks, or
- ALT or AST >3 × ULN in conjunction with elevated total bilirubin >2 × ULN or INR >1.5, or
- ALT or AST >3 × ULN with appearance of fatigue, nausea, vomiting, right upper quadrant pain or tenderness, fever, rash and/or eosinophilia (>5%).
- 3. Lost to follow-up. The subject did not return to the clinic and attempts to contact the subject were unsuccessful. Attempts to contact the subject must be documented.
- 4. Voluntary withdrawal. The subject (or subject's legally acceptable representative) wishes to withdraw from the study. The reason for withdrawal, if provided, should be recorded in the eCRF.

Note: Attempts should be made to determine the underlying reason for the withdrawal and, where possible, the primary underlying reason should be recorded (e.g., withdrawal due to an AE; withdrawal due to relocation).

5. The sponsor, IRB, IEC, or regulatory agency terminates the study.

Additionally, the Investigator should consider discontinuation of study drug and/or withdrawal from the study for subjects with a major protocol deviation, including violation of protocol entry criteria, such that continuation on study poses an unacceptable risk to the subject's health or to the study's scientific objectives.

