9.3.1.2 Study Visit, Baseline and Randomization (Day 0)

All eligible subjects who are being enrolled will present to their local site for a Baseline and Randomization visit. Baseline efficacy and safety assessments will be performed, including (but not limited to) UPDRS, CGI, PGI, Questionnaire for Impulsive-Compulsive Disorders (QUIP).

Following baseline assessments, subjects' treatment assignment will be randomized using the online interactive response system.

Arrangements will be made for the subject to attend their Day 1 visit.

9.3.1.3 Study Visit, Day 1

A urine hCG pregnancy test will be performed for female subjects of childbearing potential; pregnant women must not receive study drug.

The first dose of study drug (CVN424 or placebo) will be administered under direction of site personnel. Subjects not randomized to placebo will initiate treatment with 50 mg CVN424. Vital signs will be assessed hourly through at least 3 h post-dose. Orthostatic vital signs (non-triplicate) will be recorded pre-dose and at 3 h post-dose. Triplicate ECG will be obtained prior to dosing and approximately 3 h post-dose. Additional monitoring of vital signs and ECGs may continue beyond 3 h post-dose at the discretion of the Investigator.

Investigator or their delegate will manage incident AEs according to their medical judgment. The first dose of CVN424 may elicit an increase in body temperature and heart rate lasting several hours. These signs can be expected to spontaneously resolve within 24 h post-dose, and to lessen with repeated dosing. Antipyretic medication (e.g., Acetaminophen Extended Release Caplets, 650 mg) can be administered for symptomatic relief of fever.

A blood sample for PK analysis will be collected pre-dose and at 3 h post-dose, according to Table 5.

Subjects will be given a 10 day supply of study drug (as suspension in amber colored bottles) to be taken home and stored under refrigeration until use. Study drug will be self-administered each morning through Day 27 ± 1 day.

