9.3.1.4 Study Visit, Day 8 ± 2 days

All subjects will present to their local site on Day 8 ± 2 days, returning to the site all bottles of study medication, whether empty or unused.

Subjects will not take study drug at home on the morning of the Day 8 Study Visit. Administration of the daily dose of study drug will be deferred until after collection of a blood sample for determination of the study drug "trough" concentration.

Beginning on Visit Day 8, the high-dose cohort will increase their dosage to 150 mg CVN424 per day. This step-wise increase is intended to limit the changes that the first dose of 150 mg CVN424 may elicit in vital signs (notably, increased temperature and heart rate, which were dose-dependent and not clinically significant in a healthy volunteer study). The low-dose arm will continue to receive 50 mg per day.

Study No. CVN424-201 Page 44 of 73

Protocol v. 4.0 14 July 2021

Vital signs will be assessed hourly through at least 3 h post-dose. Orthostatic vital signs (non-triplicate) will be recorded pre-dose and at 3 h post-dose. Triplicate ECG will be obtained prior to dosing and approximately 3 h post-dose. Investigator or their delegate will manage incident AEs according to their medical judgment. Additional monitoring of vital signs and ECGs may continue beyond 3 h post-dose at the discretion of the Investigator.

A blood sample for PK analysis will be collected pre-dose and at 3 h post-dose, according to Table 5. During blood sampling, one additional tube of blood plasma will be collected for archiving (frozen storage) to support potential post hoc laboratory testing (e.g., biomarkers, potential characterization of unknown CVN424 metabolites).

After safety assessments, subjects will be given a 10 day supply of study drug to be taken home and stored under refrigeration until use.

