9.3.1.7 Study Visit, Day 27 ± 1 day

All subjects will present to their local site on Day 27 ± 1 day, returning to the site all bottles of study medication, whether empty or unused.

An untimed blood sample for PK analysis will be collected.

All subjects will have completed a Patient Motor Diary recording their capabilities, limitations and motor symptoms over the prior 2 days (e.g., Days 25 and 26). Site will conduct assessments to

Study No. CVN424-201 Page 45 of 73

Protocol v. 4.0 14 July 2021

complete the UPDRS. PGI, CGI, Epworth Sleepiness Scale, and Questionnaire for Impulsive-Compulsive Disorders.

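### No liver chemistry is scheduled between the Day 8 step-up and Day 27, so scheduled tests cannot trigger the Section 7.5 stopping criteria for a symptom-free elevation that starts on 150 mg

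*Combined protocol and SAP*

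**What the plan says.** Appendix A, footnote (c), states that hematology, serum chemistry, urinalysis and endocrine tests "will be collected at Screening, Baseline, Day 8, Day 27, Day 35, and Early Termination". The table row has no laboratory mark at Day 15 or Day 22. It does have one at Day 1, but the footnote assigns only a pregnancy test to that visit: "Urine hCG pregnancy test will be performed on female subjects of childbearing potential on Day 1 prior to dosing". Section 9.3 defers to Appendix A for the full schedule.

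On dosing, Section 9.3.1.4 says "Beginning on Visit Day 8, the high-dose cohort will increase their dosage to 150 mg CVN424 per day"; both active arms take 50 mg before that. The end of dosing is given in two ways. Section 9.3.1.3 (Day 1 visit) says "Study drug will be self-administered each morning through Day 27 ± 1 day", while Appendix A, footnote (g), says "Study drug will be self-administered each morning on days 2-28". Section 9.3.1.7 says "All subjects will present to their local site on Day 27 ± 1 day, returning to the site all bottles of study medication".

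On liver rules, Section 7.5 lists four ALT/AST criteria that call for immediate discontinuation whenever they arise on study drug. One is an elevation above 5 × ULN that "persists for more than 2 weeks". Section 6.3.1 lists study-level triggers that count affected subjects. Section 9.1.8 allows extra tests at the investigator's discretion and calls for a retest within 7 days once ALT or AST exceeds 3 × ULN.

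The laboratory part of the secondary safety endpoint (Section 5.2.2) is "Percentages of subjects with abnormal and clinically significant (CS) safety laboratory test results, ECG test results, or vital sign measurements at least once post-dose".

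**The concern.** A stopping rule based on laboratory values can act only on a result that exists while there is still drug to stop. At least two of the four Section 7.5 criteria (above 8 × ULN, and above 5 × ULN for more than two weeks) have no symptom component, so only a blood test can reveal them. If the schedule holds no test between the start of 150 mg and the end of dosing, those criteria depend on someone ordering a test for another reason.

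Safety and tolerability are the primary objective, and this is the first study in patients with Parkinson's disease. The repeat-dose experience in humans that the protocol reports is 7 daily doses in healthy volunteers. The high-dose arm takes its eighth 150 mg dose at about Day 15, so most of its time on 150 mg lies beyond that experience. There is no study safety committee; review falls to the Medical Monitor and the sponsor's Responsible Medical Officer. The same gap also limits what the laboratory data can say about the difference between the two doses.

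**Working it through.** **Inputs.** Laboratory visits: Screening, Day 0, Day 8 (±2), Day 27 (±1), Day 35 (±2) and Early Termination (Appendix A). Step-up: Day 8 (±2) visit (Section 9.3.1.4). Last dose: Day 27 ±1 (Section 9.3.1.3) or Day 28 (Section 6.2; Appendix A, footnote (g)). Half-life: about 33 h (Section 6.2).

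**1. The plan's own figure: is Day 35 on treatment?** Section 6.2 puts washout from Day 28 to Day 35 at about 5 half-lives. (35 − 28) × 24 / 33 = 5.09, which reproduces it; 0.5^5.09 ≈ 3% of drug remains. Across the windows the figure runs from (33 − 28) × 24 / 33 = 3.6 to (37 − 26) × 24 / 33 = 8.0. Day 35 is an off-treatment sample.

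**2. Gap without scheduled chemistry.** Nominal: 27 − 8 = 19 days. Shortest: 26 − 10 = 16. Longest: 28 − 6 = 22. On the nominal schedule, 19 daily doses of 150 mg (Days 8 to 26) are taken before the Day 27 visit.

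**3. What each scheduled post-dose sample reflects in the high-dose arm.**
- Day 8: 50 mg, or at most hours at 150 mg. The documents do not say whether this chemistry is drawn before or after the day's dose.
- Day 27: established 150 mg dosing.
- Day 35: washout (step 1).

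That is three post-dose samples: two on treatment, of which one is at established 150 mg.

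**4. Can a scheduled result prompt a Section 7.5 stop on 150 mg?** The first scheduled result after the step-up comes from the Day 27 visit, where all bottles are returned. If dosing runs to Day 28, at most 28 − 27 = 1 dose remains (2 if the visit falls on Day 26). An Early Termination sample follows a decision to stop and cannot prompt it.

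**5. The two-week persistence criterion.**
- Elevation found at Day 8 and retested under Section 9.1.8: 8 + 14 = 22, so more than two weeks is reached at about Day 23 (Day 21 to 25 with the window). This is before dosing ends, and the criterion can be met.
- Elevation first found at Day 27: 27 + 14 = 41, so persistence cannot be shown until after Day 41. That is past the end of dosing and past the Day 35 final visit. The scheduled Day 27 and Day 35 samples are only 8 days apart (33 − 28 = 5 to 37 − 26 = 11).

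**6. Illustration only.** Assume that onset is uniform over Days 8 to 27 and that an elevation lasts d days. Neither assumption comes from the documents. The Day 27 sample then catches a fraction d/19:

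| Duration d (days) | Caught at Day 27 |
|---|---|
| 5 | 26% |
| 7 | 37% |
| 10 | 53% |
| 14 | 74% |

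Those that are caught are still found only at the end of dosing.

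**The case against.** The strongest reply is that Section 7.5 sets out when drug must be stopped, not how often to test, so the documents do not literally contradict each other. That is correct, and testing frequency is a clinical judgement. Section 4.1 also reports no treatment-related laboratory trends in phase 1 (up to 7 daily doses of 150 mg) and minimal animal toxicity. These points bear on how likely an elevation is. They do not show that the rule can act if one occurs.

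Three stronger readings are tempting, and the documents do not support them.

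- *The liver rules cannot operate at 150 mg.* The Section 6.3.1 triggers count across subjects and carry no on-treatment condition. Day 27, Day 35 or Early Termination results from earlier subjects can start a review while later subjects are being dosed. At subject level, AEs are assessed at every visit, one Section 7.5 criterion pairs symptoms with ALT/AST above 3 × ULN, and Section 9.1.8 allows unscheduled tests.
- *The two-week criterion can never be met before dosing ends.* It can, for an elevation found at Day 8 and retested (step 5 of the working).
- *The high-dose laboratory endpoint rests on one on-treatment sample.* Section 5.2.2 counts any post-dose result, so Days 8, 27 and 35 all contribute. All arms share the schedule, so the gap by itself does not bias the comparison between arms.

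The provisions in Section 9.1.8 do not close the remaining gap. The 7-day retest starts only after an elevation has been found, and discretionary testing needs a reason to test. An elevation without symptoms that begins after the step-up supplies neither.

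**Conclusion.** The point holds in a limited form. No liver chemistry is scheduled for 19 days (16 to 22) between the Day 8 visit and the Day 27 visit, which covers essentially all dosing at 150 mg. For an ALT/AST elevation without symptoms that starts after the step-up, scheduled tests cannot trigger the subject-level stopping criteria of Section 7.5 during 150 mg dosing. If the elevation is first found at Day 27, the two-week criterion cannot be met on treatment.

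One of the three scheduled post-dose samples reflects established 150 mg dosing, so Day 27 is the only scheduled on-treatment laboratory comparison of 50 mg with 150 mg. An elevation that begins after Day 8 and resolves before Day 27 would go unseen unless an unscheduled test were done.

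This rests on reading the Day 1 table mark as the pregnancy test only, as footnote (c) states, and on the safety assessments mentioned for Days 15 and 22 including no laboratory tests, since none are named there and Appendix A marks none. It does not depend on any assumed rate of liver injury.

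**What to change.** Reconcile the laboratory schedule in Appendix A, footnote (c), with Section 7.5 so that the subject-level liver criteria can act on scheduled results during the 150 mg period. PK blood is already drawn at the Day 15 and Day 22 visits (Section 9.1.13, Table 5), so this can be done without an extra visit or venepuncture. Which visit or visits to use is for the sponsor's clinical team. The cost is an extra tube and central-laboratory fees.

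In the same amendment, at the cost of wording only:
- state whether the Day 8 chemistry is drawn before or after that day's dose;
- reconcile the two statements of when dosing ends (Section 9.3.1.3 against Appendix A, footnote (g));
- reconcile the Day 1 laboratory mark in the table with footnote (c);
- correct the cross-reference in Section 9.1.8, which sends the reader to Section 7.4 (diet and fluids) for the discontinuation criteria that are in Section 7.5.

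A note in the report that laboratory findings at 150 mg rest on one scheduled sample would be accurate, but would not by itself let the stopping criteria act.
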